9 PRIOR AND CONCOMITANT ILLNESSES AND TREATMENTS

9.1 Prior and concomitant illnesses

Additional diseases present at the time of signing the informed consent are regarded as concomitant diseases and must be documented in the eCRF. Relevant past diseases must also be documented in source data and in the medical history section of the eCRF.

Illnesses first occurring or detected during the study, and worsening of a concomitant disease during the study, are to be regarded as AEs and must be documented in source data and in the AE section of the eCRF (see Section 11).

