11 ADVERSE EVENTS

11.1 Definitions

11.1.1 Adverse events

Adverse event means any untoward medical occurrence associated with the use of a drug in humans, whether or not considered drug related. This includes any unfavorable and unintended sign, symptom, syndrome, or illness that develops or worsens during the clinical study whether or not related to the investigational products and the study procedures.

For the purpose of the study, clinically significant abnormal results of diagnostic procedures including abnormal laboratory findings (e.g. requiring unscheduled diagnostic procedures or treatment measures or resulting in withdrawal from the study) discovered at screening will be related to medical history or are considered to be AEs if they are detected post screening. Any AEs first occurred or worsened in severity post treatment are considered as treatment-emergent adverse event (TEAE).

Maximum severity should be assigned to one of the following categories:

- **Mild:** For example, an AE which is easily tolerated by the subject, causing minimal discomfort and not interfering with everyday activities.
- **Moderate:** For example, an AE which is sufficiently discomforting to interfere with normal everyday activities.
- **Severe:** For example, an AE which is incapacitating and prevents normal everyday activities.

Worsening of a sign or symptom of the condition under treatment will be recorded as AE and if this worsening matches any criterion for an “SAE”, it must be recorded as such (see Section 11.1.2).

Examples of AEs include one of the following or a combination of two or more of these factors:

- A new sign, symptom, illness, or syndrome.
- Worsening of a concomitant or pre-existing illness.
- An effect of the IMP or concomitant medication.
- An effect of the IMD, if applicable
- An effect of an invasive procedure required by the protocol.
- An accident or injury.

AEs can be categorized as “non-serious” and “serious” (see Section 11.1.2).

Surgical procedures themselves are not AEs; they are therapeutic measures for conditions that require surgery. The condition for which the surgery is required is an AE, if it occurs or is detected during the study period. Planned surgical measures and the condition(s) leading to these measures are not AEs, if the condition(s) was (were) known before the study period (see

Section 9.1) and do not worsen during the study. In the latter case, the condition should be reported as medical history.

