11.2 Period of AE collection

Collection of AEs starts with signing the informed consent documents until the end of the study. AEs will be discriminated as AEs and TEAEs.

- AEs developing between signing the ICF until Visit 2 with a suspected causal relationship to any study procedures will be considered and documented as an AE.
- Collection of TEAEs extends from Visit 2 (baseline) until end of the study at Visit 3.
- If the investigators detect an SAE in a subject after end of study, and considers the event possibly related to prior study treatment or procedures, they should report this event to the pharmacovigilance department of the sponsor (see section 11.3.1).

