14.1 Analysis variables

The primary endpoints for pharmacokinetics are the

- Baseline-adjusted plasma concentrations of ALA for obtaining baseline-adjusted plasma concentration-time curves
- Baseline-adjusted plasma concentrations of PpIX for obtaining baseline-adjusted plasma concentration-time curves

Secondary endpoints are the

- Baseline-adjusted AUC_{0-t} , baseline-adjusted $AUC_{0-\infty}$, baseline-adjusted C_{max} , T_{max} , $T_{1/2}$, and λ_Z for ALA (if data permit)
- Baseline-adjusted AUC_{0-t} , baseline-adjusted $AUC_{0-\infty}$, baseline-adjusted C_{max} , T_{max} , $T_{1/2}$, and λ_Z for PpIX (if data permit)
- Assessment of safety and tolerability of PDT with BF-200 ALA under maximal use conditions, including:
 - Frequency and severity of treatment-emergent adverse events (TEAEs), including serious adverse events (SAEs). TEAEs are defined as all AEs with onset or worsening after treatment with the investigational medicinal product and device.
 - Overall tolerability.
 - Application site skin reactions in the treatment field(s) during and post PDT.
 - Application site discomfort during and after illumination reported by the subjects.
 - Application site pain during PDT on an 11-point Numeric Rating Scale (NRS-11).
 - Vital signs data.
 - Safety laboratory data if clinically significant deviations occur.
 - Data from the physical examinations if clinically significant findings occur.

Tertiary endpoints are the

- Unadjusted plasma concentration-time curve for ALA and pharmacokinetic parameters of ALA: unadjusted AUC_{0-t} , unadjusted $AUC_{0-\infty}$, unadjusted C_{max} , T_{max} , $T_{1/2}$, and λ_Z if data permit

- Unadjusted plasma concentration-time curve for PpIX and pharmacokinetic parameters of PpIX: unadjusted AUC_{0-t} , unadjusted $AUC_{0-\infty}$, unadjusted C_{max} , T_{max} , $T_{1/2}$, and λ_z if data permit

All pharmacokinetic characteristics (AUC_{0-t} , $AUC_{0-\infty}$, $T_{1/2}$ and λ_z) will be derived from baseline-adjusted as well as unadjusted plasma concentrations of ALA and PpIX as described above.

The pharmacokinetic parameters for ALA and PpIX will be derived from plasma using noncompartmental methods and are listed in Table 6. Values < LLOQ and negative values after baseline adjustment are set to zero and disregarded when displaying data on a logarithmic scale.

Table 6: List of pharmacokinetic parameters

Parameter	Description
C_{max}	Observed maximum baseline-adjusted or unadjusted plasma concentration

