4.4.2 Analysis of Secondary Endpoints

Frequency and severity of TEAEs / Overall tolerability

AEs will be coded by using the Medical dictionary for regulatory activities (MedDRA). The latest MedDRA version at the day of data base closure will be used. If an AE occurs in multiple treatment fields, it is reported separately for each treatment field within the eCRF. Thus, some AEs are counted repeatedly for the analysis.

Analysis will focus on TEAEs. TEAEs are defined as all AEs or SAEs that occur after lesion preparation at Visit 2, which is at maximum one hour before IMP application (i.e. AE onset date/time \geq date/time of IMP application (Visit 2) – 1h).. If unclear due to incomplete start date/time of AE or IMP application, AEs will be assumed as TEAEs.

TEAEs will be tabulated by system organ class (SOC) and preferred term (PT) (MedDRA). The number of entries, as well as the number and rate of affected subjects will be reported for each treatment area and overall.

TEAEs will also be tabulated by relationship to IMP and/or medical device and by intensity.

TEAEs leading to death, serious TEAEs, TEAEs related to IMP, and TEAEs related to medical device will be presented separately.

TEAEs are considered being related to IMP or medical device, if causal relationship between IMP or medical device and the TEAE is at least possible or relationship assessment is missing.

AEs which occurred before lesion preparation, which is at maximum one hour before IMP application (i.e. AE onset date/time < date/time of IMP application (Visit 2) - 1h) will be listed separately but are not included in any other tables or listings.

Application site skin reactions in the treatment field(s) during and post PDT

The frequency of application site skin reactions for each category (erythema, edema, induration, vesicles, erosion, ulceration, scaling/flaking, scabbing/crusting, discharge/exudate, other) will be presented by intensity and treatment area.

Application site discomfort during and after illumination reported by the subjects

The frequency of application site discomfort for each category (burning, itching, pain, stinging, warmth, other) will be presented by intensity and treatment area.

Application site pain during PDT

Subjects will assess the maximum pain experienced during PDT using an 11-point Numeric Rating Scale (NRS-11) ranging from 0 (no pain at all) to 10 (worst possible pain). Basic statistics for application site pain will be given.

Vital signs

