--------------------------------	----------------------------

All tables, listings, and graphs will be generated in A4 paper format.

[figure not shown]
The statistical evaluation will be performed using SAS version 9.4 or higher.

5 Changes from Protocol

In the following any changes on statistical aspects as described in the protocol are given:

- The protocol version 2.0 of 17Jan2020 states in section 14.3, that confidence intervals will be presented for maximal pain score. As all planned analyses are of exploratory nature and without any formal statistical hypotheses, no confidence intervals will be conducted.
- In addition to the analysis sets specified in protocol version 2.0 of 17Jan2020, the analysis set 'Enrolled 2' is defined.

6 Signatures

Statistician:

Date (ddmmmyyyy)
Signature

Sponsor:
 Biofrontera Bioscience GmbH Head Clinical Trial Project Management [name] [name] Germany
Date (ddmmmyyyy)
Signature

Sponsor:
 Biofrontera Bioscience GmbH Project Manager Clinical Trials [name] [name] Germany
Date (ddmmmyyyy)
Signature

TITEL PAGE SAP PK, V2.0 DATED 21-SEP-2020

Study ALA-AK-CT015,

NCT04319159

An open-label Phase I study to evaluate the pharmacokinetics of 5-aminolevulinic acid and protoporphyrin IX in human plasma under maximal use conditions after topical application of 3 tubes of BF-200 ALA 10% gel for photodynamic therapy (PDT) in subjects suffering from actinic keratosis

Statistical Analysis Plan for Pharmacokinetics

Study title: An open-label Phase I study to evaluate the pharmacokinetics of 5-aminolevulinic acid and protoporphyrin IX in human plasma under maximal use conditions after topical application of 3 tubes of BF-200 ALA 10% gel for photodynamic therapy (PDT) in subjects suffering from actinic keratosis

Protocol Number: ALA-AK-CT015

Version: Final 2.0
Date: 21-SEP-2020

PREPARED BY:

Senior Biostatistician

Date

REVIEWED BY:

Team Lead Programming

Date

APPROVED:

Director of Exploratory Development
Biofrontera Bioscience GmbH

Date

INDEX

1. INTRODUCTION	3
2. RESPONSIBILITIES	3
3. STUDY OBJECTIVES AND ENDPOINTS.....	3
4. DESIGN OF THE STUDY	4
5. SAMPLE SIZE AND POWER ESTIMATION.....	4
6. ANALYSIS SETS	4
7. PRESENTATION OF DATA	5
8. SOFTWARE	5
9. DEMOGRAPHIC DATA AND BASELINE CHARACTERISTICS.....	5
10. PHARMACOKINETIC PARAMETERS.....	5
10.1. Tabulation of Individual Data	7
11. STATISTICAL METHODOLOGY FOR PHARMACOKINETIC ENDPOINTS	7

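### The safety SAP classifies treatment-emergent AEs by onset alone, omits the protocol's worsening criterion, and declares neither that nor the earlier start of its window

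*SAP*

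**What the plan says.** The protocol defines a TEAE twice, and both definitions include worsening. Section 11.1.1 has: "Any AEs first occurred or worsened in severity post treatment are considered as treatment-emergent adverse event (TEAE"). Section 14.1, which names the safety endpoints, has: "TEAEs are defined as all AEs with onset or worsening after treatment with the investigational medicinal product and device".

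Safety SAP 4.4.2 says: "TEAEs are defined as all AEs or SAEs that occur after lesion preparation at Visit 2". It turns this into a rule on one variable. An AE is treatment-emergent if its onset date/time is no earlier than the time of IMP application minus 1 h, the hour being the longest allowed gap between lesion preparation and application. AEs with earlier onset "will be listed separately but are not included in any other tables or listings".

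SAP section 5 (Changes from Protocol) opens with: "In the following any changes on statistical aspects as described in the protocol are given". It has two entries: no confidence intervals for the maximal pain score, and the additional set Enrolled 2. The TEAE definition is not among them.

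Three protocol statements limit the reach of the difference. For the period before treatment, section 11.2 speaks of "AEs developing between signing the ICF until Visit 2 with a suspected causal relationship to any study procedures". New illnesses and, in section 9.1, "worsening of a concomitant disease during the study, are to be regarded as AEs". Section 11.1.1 adds: "Worsening of a sign or symptom of the condition under treatment will be recorded as AE".

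**The concern.** Frequency and severity of TEAEs is a named secondary endpoint, and SAP 4.4.2 builds its TEAE tables on the onset test. An event that the protocol calls treatment-emergent can therefore be missing from all of them: system organ class and preferred term, relationship, intensity, and serious TEAEs. Protocol 11.3.1.1 foresees a non-serious AE becoming serious. If that happened through worsening after PDT, and the AE had begun before the cutoff, the onset test would keep it out of the serious-TEAE table as well.

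The SAP's rule for unclear dates does not help. It defaults to TEAE only when the timing cannot be determined, and here the onset date is known. A reader of the report would assume the protocol definition, because section 5 reports no change to it.

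**Working it through.** The plan gives no figure to reproduce on this point. The check applies both definitions to example AEs and then bounds the effect.

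**Step 1: the two rules side by side.** Protocol 11.1.1 and 14.1: onset or worsening after treatment. SAP 4.4.2: onset at or after IMP application minus 1 h.

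| Example AE | Protocol 11.1.1 / 14.1 | SAP 4.4.2 |
|---|---|---|
| A. Onset 5 days before IMP, worsens 1 day after, one record | TEAE | Not a TEAE; separate listing only |
| B. Onset 30 min before IMP | Not a TEAE | TEAE |
| C. Onset 1 h after IMP | TEAE | TEAE |
| D. Concomitant disease worsens 1 day after IMP, entered as its own AE | TEAE | TEAE |

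The rules differ in A (worsening dropped) and B (window starts up to 1 h earlier). Neither difference is in section 5. B agrees with the SAP's safety set, which begins at preparation of the treatment field, and it is the more inclusive choice. It needs declaring, not reversing.

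**Step 2: does the protocol turn case A into case D?** Sections 9.1 and 11.1.1 make worsening of a concomitant disease or of the treated condition an AE in itself. No section requires a new record when an AE already on file worsens. Section 11.1.1 assigns one maximum severity to an AE, which is compatible with a single record that keeps its first onset date.

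**Step 3: can worsening be dated from the AE record?** The AE details required by Protocol 11.3 include start and stop date and time, intensity, outcome, seriousness and relatedness. A date of worsening is not among them.

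**Step 4: how many events?** Visit 1 is up to 14 days before PDT, and Visit 2 may be moved once by up to 14 days, so the window is 14 + 14 = 28 days. Section 11.2 restricts AEs in it to those suspected to be related to study procedures. Dosing-day exclusion criterion 2 also bars treatment when sunburn, wounds, irritations or other confounding skin conditions are present in the illumination areas. A local pre-treatment event that PDT could aggravate should therefore seldom be ongoing at dosing.

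**Step 5: effect of one event.** Recruitment to a stratum stops at 16 treated subjects (Protocol 7.2), 32 in total. One subject reclassified for one preferred term changes the subject rate by at most 1/16 = 6.25% (6.3 percentage points) in the stratum and 1/32 = 3.1 percentage points overall. The change is zero if that subject already has a TEAE with the same term.

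**The case against.** The strongest defence is that the protocol already treats worsening as an event of its own, so the SAP's onset rule captures most of it. This stands for concomitant disease and for the condition under treatment, provided each is entered with its own onset. Protocol 11.2 also separates AEs from TEAEs by collection period, from Visit 2 onward, which is close to what the SAP does. The SAP is otherwise inclusive: it counts from lesion preparation and resolves unclear dates in favour of TEAE. The excluded events remain listed, and the study is descriptive, with no hypotheses. All of this limits the size. It does not settle the already recorded AE that worsens on the same record, nor the silence of section 5.

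A reader might infer more from the same SAP section: that recording an AE once per treatment field, with no maximum-intensity rule in view, distorts the intensity and application-site tables. The documents do not support that as a finding. The SAP discloses the repeated counting. It states that entries and affected subjects are both reported for the system organ class and preferred term table, and the sentence on intensity tables follows directly. Table descriptions are in Appendix A, which is not in the supplied text, and the standard table format announced in SAP 4.7 is also missing from it. SAP 4.7 allows other formats as well. The most that can be asked is that someone check Appendix A for the counting unit.

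**Conclusion.** The point holds and is minor. The SAP's TEAE rule is narrower than the protocol's on worsening and slightly wider at the start of the window, and both differences are undeclared. The affected case is specific: onset before the cutoff, still ongoing, worse after PDT, and kept on one record.

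Two stronger readings should be avoided. The SAP does not lose all post-treatment worsening, because worsening entered as a new AE is counted. Nor are the affected events hidden, because they appear in the separate listing.

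The expectation of few events assumes that the restriction in Protocol 11.2 governs what is recorded before Visit 2. Section 9.1 is worded more broadly and, if the site follows it, could yield more pre-treatment AEs. The documents give no count of such AEs, so only the per-event bound (6.3 percentage points per stratum, 3.1 overall) can be stated.

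**What to change.** 1. In SAP 4.4.2, extend the TEAE rule with: *or worsening in severity after the start of the PDT procedure*.
2. Make it workable. Instruct the site to enter any post-treatment worsening of an already recorded AE as a new AE record with its own onset date/time. The onset test then classifies it correctly.
3. Where that was not done, add an item to the data review in SAP 4.6: before database lock, identify AEs that began before the cutoff, were ongoing at PDT and worsened afterwards, and count them as TEAEs. Source notes and the eCRF audit trail described in Protocol 17.1 may help to find them.
4. In SAP section 5, declare that the TEAE window starts at lesion preparation (IMP application minus 1 h), earlier than in Protocol 11.1.1 and 14.1.

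The cost is a few lines of SAP text, one site instruction or one data-review listing, and a small change to the derivation of the TEAE flag. No new assessments are needed. Because the required AE details contain no date of worsening, item 1 cannot be programmed from them without item 2 or 3.

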4.4.3 Analysis of Tertiary Endpoints

The analysis of pharmacokinetics is described in a separate SAP.

4.5 Missing Values

No missing value imputation method will be applied. In case an AE cannot clearly assigned as TEAE yes/no due to partial or completely missing AE/IMP application dates, it will be considered as TEAE.

4.6 Data Base Closure and Data Review

A data base closure will be performed prior to the analysis. All parameters will be checked, as specified in the data validation plan, and all queries resolved before data base closure and analysis.

SDTM datasets will be used to create ADaM datasets using ADaM Implementation Guide [REDACTED] and Analysis Data Model [REDACTED]. An ADaM specification document will be set-up as a MS Excel spreadsheet, describing ADaM dataset to be created. A final define.xml will be created when the ADaM datasets and the specification documents are final.

[figure not shown]
A data review will be conducted prior to data base lock based on all data to allocate the subjects to the analysis sets. Furthermore, the following items will be discussed:

- Any violation of inclusion/exclusion criteria
- Any dose changes/incompliance to study therapy
- Informed consent date not before application of IMP date or any other study related procedure
- Discrepancies between actual and planned treatment area
- Use of forbidden medication
- Premature discontinuation during the study
- Sample processing errors that may lead to inaccurate bioanalytical results

These evaluations and assessments will be done together and in agreement with the Sponsor, however [REDACTED] will provide the Sponsor with the appropriate subject listings (as defined in appendix A). Data review will be done via a telephone conference. All protocol deviations detected during DRM will be listed.

4.7 Miscellaneous

For qualitative variables the frequencies (absolute and relative) are calculated. If no further remark is given in the description of the tables, following format will be used for all tables with qualitative variables:

For this standard format the description of the tables in Appendix A determines only the X- and Y-variables. If another format of table is described in the details to the tables, the real design will be determined by the technical possibilities within SAS and may not look identical to the provided example. However, all information as displayed will be included.

Quantitative parameters will be described by declaring the mean value, standard deviation, minimum, first quartile, median, third quartile, and maximum. In the description of the tables this will be denoted by „basic statistics“. In general, minimum and maximum will be presented to the same level of precision as the raw data; means and medians, standard deviation, and quartiles will be presented to one further decimal place.

For frequency tables, missing values (including user-defined missing values) will not be included in the calculation of percentages. Percentages will be presented to one decimal place.

The listings are always sorted by treatment area and subject. If a different sorting order should be used for some listings this will be remarked separately. The variables for the special listings are explicitly given in the description of listings. All listings will be presented for the safety analysis set, if not stated differently.

For screening failures, demographic data, date of informed consent as well as date and reason for withdrawal will be entered into the clinical database and will not be passed through the data cleaning process. Enrolled but not treated subjects (e.g. withdrawal before treatment) will be considered in tables and listings describing analysis sets, eligibility, and visits, as well as listings for subject demographics and discontinuation. Listings including enrolled but not treated subjects will be stratified by SAF.

The following title will be used for all generated tables, listings, and graphs:

ALA-AK-CT015-maxuse-pk-ak	Page # of #
[REDACTED]	
[REDACTED]	
[REDACTED]	

The numbering NNN of the tables/listings/graphs will be stated in the detailed description (Appendix A).

Following footnote will be used for all generated tables, listings, and graphs:

Date: <Actual date(ddmmmyyyy)>	Program: <Name of program>
--------------------------------	----------------------------

All tables, listings, and graphs will be generated in A4 paper format.

[figure not shown]
The statistical evaluation will be performed using SAS version 9.4 or higher.

5 Changes from Protocol

In the following any changes on statistical aspects as described in the protocol are given:

- The protocol version 2.0 of 17Jan2020 states in section 14.3, that confidence intervals will be presented for maximal pain score. As all planned analyses are of exploratory nature and without any formal statistical hypotheses, no confidence intervals will be conducted.
- In addition to the analysis sets specified in protocol version 2.0 of 17Jan2020, the analysis set 'Enrolled 2' is defined.

6 Signatures

Statistician:

Date (ddmmmyyyy)
Signature

Sponsor:
 Biofrontera Bioscience GmbH Head Clinical Trial Project Management [name] [name] Germany
Date (ddmmmyyyy)
Signature

Sponsor:
 Biofrontera Bioscience GmbH Project Manager Clinical Trials [name] [name] Germany
Date (ddmmmyyyy)
Signature

TITEL PAGE SAP PK, V2.0 DATED 21-SEP-2020

Study ALA-AK-CT015,

NCT04319159

An open-label Phase I study to evaluate the pharmacokinetics of 5-aminolevulinic acid and protoporphyrin IX in human plasma under maximal use conditions after topical application of 3 tubes of BF-200 ALA 10% gel for photodynamic therapy (PDT) in subjects suffering from actinic keratosis

Statistical Analysis Plan for Pharmacokinetics

Study title: An open-label Phase I study to evaluate the pharmacokinetics of 5-aminolevulinic acid and protoporphyrin IX in human plasma under maximal use conditions after topical application of 3 tubes of BF-200 ALA 10% gel for photodynamic therapy (PDT) in subjects suffering from actinic keratosis

Protocol Number: ALA-AK-CT015

Version: Final 2.0
Date: 21-SEP-2020

PREPARED BY:

Senior Biostatistician

Date

REVIEWED BY:

Team Lead Programming

Date

APPROVED:

Director of Exploratory Development
Biofrontera Bioscience GmbH

Date

INDEX

1. INTRODUCTION	3
2. RESPONSIBILITIES	3
3. STUDY OBJECTIVES AND ENDPOINTS.....	3
4. DESIGN OF THE STUDY	4
5. SAMPLE SIZE AND POWER ESTIMATION.....	4
6. ANALYSIS SETS	4
7. PRESENTATION OF DATA	5
8. SOFTWARE	5
9. DEMOGRAPHIC DATA AND BASELINE CHARACTERISTICS.....	5
10. PHARMACOKINETIC PARAMETERS.....	5
10.1. Tabulation of Individual Data	7
11. STATISTICAL METHODOLOGY FOR PHARMACOKINETIC ENDPOINTS	7
